2.7.6.2 Patient ADA status

The following overall summaries will be provided using the Immunogenicity incidence set:

- Treatment-boosted ADA-positive: number and percent of patients with at least one treatment-boosted ADA-positive sample. The denominator is the number of patients with an ADA-positive sample at baseline.
- Treatment-induced ADA-positive: number and percent of patients with at least one treatment-induced ADA-positive sample. The denominator is the number of patients with an ADA-negative sample at baseline.
- ADA-negative: number and percent of patients with no treatment-induced or treatment-boosted ADA-positive sample.

- ADA incidence (i.e. % ADA-positive): number and percent of patients with at least one treatment-induced or treatment-boosted ADA-positive sample.

The following summaries, both overall and by timepoint (including baseline), will be provided using the Immunogenicity prevalence set. For summaries by timepoint, the denominator is the number of patients at that timepoint with determinant samples:

- ADA prevalence: number and percent of patients with at least one ADA-positive sample.
- NAb ADA prevalence: number and percent of patients with at least one ADA-positive NAb sample.

A listing will be provided by subject with supporting information (i.e. ADA sample status at each timepoint (including positive samples) and patient ADA status

2.7.7 Exposure to Investigational Product

Descriptive statistics will be produced to describe the exposure to investigational product by treatment group and by phases. The number and percentage of subjects with dose change, reason for dose change and duration of exposure to investigational product in days will be summarized by treatment group.

2.7.8 Summary Concomitant Medication Use

The number and proportion of subjects receiving headache-related medications will be summarized by acute medication category for each treatment group.

[REDACTED]

[REDACTED]

[REDACTED]

[REDACTED]

2.10 Patient-reported outcome analyses

PRO scales were included to gather information about “impact on everyday activities” and “physical impairment” (MPFID), [REDACTED]

[REDACTED]

[figure not shown]
All variables assessing change from baseline will be calculated by subtracting the baseline score from the visit score. The baseline score will be the score recorded on Day 1 ([Section 2.1.1](#)). Change from baseline in total score (or subscale if applicable) of MPFID, [REDACTED], [REDACTED] will be analyzed similarly as the secondary analysis of continuous endpoints described in the [Section 2.6.2](#) (Analysis method IV).

[figure not shown]
[REDACTED]

In all cases, estimates (difference/or odds ratio) of treatment group compared to placebo group with associated 95% confidence intervals and p-values will be provided.

Descriptive statistics/frequency tabulations will be presented for each visit for PRO scales.

[figure not shown]

[figure not shown]

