2.1.1 General definitions

Study drug

Novartis will supply the investigational product listed below

- AMG 334 70 mg/1 mL pre-filled syringe
- Matching placebo in 1mL pre-filled syringe, identical in appearance

Two injections of AMG 334 70 mg (equaling 140 mg total dose) or placebo will be administered at each dosing visit. The matching Placebo to AMG 334 pre-filled syringe will have the same appearance as the investigational drug. Each syringe will be packaged individually in double blinded fashion for the double-blind treatment Epoch. The study treatments will be labelled as:

- AMG 334 70mg/1mL or Placebo for Double-Blind Treatment Epoch

Baseline

The baseline period for efficacy endpoints collected by the daily diary (e.g., monthly migraine days, acute migraine-specific medication days, MPFID, etc.) is defined as the period

between week -4 visit (when eDiary device is dispensed to the patient for daily data capture) and the day prior to study day 1 (study day 1 is not included).

A baseline for PRO ([REDACTED] MPFID) and safety (including C-SSRS) values refers to the last evaluable measurement prior to the first administration of the study drug, irrespective of re-screening. In this case, baseline values will be the values obtained on the day of the randomization (Day 1, Visit 101), or on an earlier visit (scheduled or unscheduled) which is the closest to Visit 101, if Visit 101 is missing or the assessment was not done at baseline.

Change from Baseline in Monthly Efficacy Measurement

The change from baseline in monthly efficacy measurement is the monthly efficacy measurement in the monthly interval prior to the given time point minus the baseline monthly efficacy measurement. Please, refer to the monthly intervals for efficacy endpoints defined in [Table 2](#). For example, change from baseline in monthly migraine days in the last month (month 3) of the double-blind epoch will be calculated based on the following:
(Monthly migraine days in the last month of the DBTE) – (monthly migraine days during the baseline phase)

If the baseline or post-baseline value is missing, then the change from baseline is set to be missing.

Percent Change from Baseline

The change from baseline divided by baseline and multiplied by 100:

$$(\text{post-baseline} - \text{baseline}) * 100 / \text{baseline}$$

50% (or 75%, 100%) response is defined as a decrease from baseline score value for at least 50% (or 75%, 100%).

Study day

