“Unable to do” and frequency items ranging from “None of the time” to “All of the time.” These are assigned scores from 1 to 5, with 5 representing the greatest burden. For each domain, the scores will be calculated as the sum of the item responses and the sum will be rescaled to a 0 - 100 scale, with higher scores representing greater impact of migraine (ie, higher burden). There will be a score for each of the two domains and a third score for the stand-alone item. The recall period is the past 24 hours. Please refer to [Section 2.10](#) and [Appendix E.1](#) for details.

Subjects will complete the MPFID every day using the eDiary during DBTE.

Monthly average MPFID score is defined as the sum of observed MPFID scores divided by the total number of observed MPFID scores between each monthly IP dose. Monthly average MPFID score at baseline is the average MPFID score in the baseline period.

Change from baseline in monthly average physical impairment scores as measured by the MPFID in the last month of the double-blind treatment epoch

Calculated based on the following: (monthly average physical impairment scores as measured by the MPFID in the last month of the DBTE) – (baseline monthly average physical impairment scores as measured by the MPFID)

Change from baseline in monthly average impact on everyday activities scores as measured by the MPFID in the last month of the double-blind treatment epoch

Calculated based on the following: (monthly average impact on everyday activities scores as measured by the MPFID in the last month of the DBTE) – (baseline monthly average impact on everyday activities scores as measured by the MPFID)

[REDACTED]

[REDACTED]

[REDACTED]

[REDACTED]

[figure not shown]
[REDACTED]

[figure not shown]
[REDACTED]

[Redacted]

[Redacted]

[Redacted]

Safety Endpoints

Treatment-Emergent Adverse Event (TEAE)

Adverse Events (AEs) recorded on the Adverse Events eCRF page that occurs on or after first dose of investigational product as determined by the flag indicating if the adverse event started prior to the first dose on the Adverse Events eCRF and up to and including 112 days after the end of IP (16 weeks after the last dose of IP).

Serious Adverse Event (SAE)

SAEs determined by the flag indicating if the adverse event is serious on the Adverse Events eCRF page will include those that occur after signing of the informed consent and up to and including end of study.

Serious Treatment-Emergent Adverse Event

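### The SAP gives the two MPFID secondary endpoints two incompatible baselines, a Baseline Epoch average and a single Day 1 score, and no visible text says which one applies

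*SAP*

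**What the plan says.** Two rules stand in the current SAP, and each names MPFID.

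**Baseline Epoch average.** The first Baseline paragraph of SAP 2.1.1 covers "The baseline period for efficacy endpoints collected by the daily diary (e.g., monthly migraine days, acute migraine-specific medication days, MPFID, etc". The period lies between the Week -4 visit "and the day prior to study day 1 (study day 1 is not included". SAP 2.1.2 follows it: "Monthly average MPFID score at baseline is the average MPFID score in the baseline period". Its physical impairment formula subtracts the "baseline monthly average physical impairment scores as measured by the MPFID", and the everyday activities formula has the same form.

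**Single score before dosing.** The next paragraph of 2.1.1 sets the baseline for PRO and safety values. Part of its PRO list is blacked out, but MPFID is visible in it. That baseline "refers to the last evaluable measurement prior to the first administration of the study drug", and "baseline values will be the values obtained on the day of the randomization (Day 1, Visit 101" or, failing that, at the closest earlier visit. SAP 2.10 repeats the rule for all change variables: "The baseline score will be the score recorded on Day 1". The next sentence there takes "Change from baseline in total score (or subscale if applicable) of MPFID" and assigns it Analysis method IV, which Table 5 also assigns to the two MPFID secondary endpoints.

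The cross-reference in 2.10 leads back to 2.1.1, which holds both rules. SAP 2.6.1, 2.6.2, 2.10.5, Table 5, section 4 and Appendix E do not choose between them. The protocol (Table 2-1 and section 9.5.1) speaks only of change from baseline to month 3.

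**The concern.** The MPFID domain changes are two of the six secondary efficacy endpoints in SAP 2.6.1. Baseline enters the analysis twice, in the change score and as a covariate (2.6.2). Section 2.10.5 rules out sensitivity analyses for PROs, so no planned output would show the effect of the choice. A programmer who followed 2.10 would be complying with the SAP, and so would one who followed 2.1.2.

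The two baselines are different measurements. One averages up to about 28 daily scores. The other is one score with a 24-hour recall. When the Day 1 score is used, the two rules share no diary entry. SAP Table 2 also starts the first post-baseline month on Study Day 1, so that entry would serve both as baseline and as part of the Week 4 average.

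**Working it through.** **Is there a figure in the plan to reproduce?** Not for MPFID. The only power statement (SAP section 3) concerns the primary responder endpoint: 110 per group, 18% against about 38%, two-sided 0.05. It recomputes to 91.6% power against the stated 90%, with odds ratio (0.38/0.62)/(0.18/0.82) = 2.79 against the stated 2.8. Nothing below changes it.

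**What a single day captures.** Eligibility requires 4 to 14 migraine days in the 4-week Baseline Epoch (protocol 4.1). A randomly chosen day is a migraine day with probability 4/28 = 14% to 14/28 = 50%. A one-day score would therefore describe a migraine-free day for about 50% to 86% of patients.

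**Noise in the baseline itself.** Assume equally correlated daily scores with correlation r and 28 observed days. Relative to one day, the variance of the average is v = r + (1 - r)/28.
- r = 0.05: v = 0.05 + 0.95/28 = 0.084, so one day has 1/0.084 = 11.9 times the variance of the average.
- r = 0.5: v = 0.5 + 0.5/28 = 0.518, ratio 1.9.

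This is the variance of the baseline, not of the treatment effect.

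**Effect on the treatment contrast.** The documents give no MPFID variance, so this step rests on assumed inputs:
- mean migraine frequency 9 per 28 days, between-patient SD 2 or 3, restricted to 4-14 observed days;
- migraine-day score with mean 35, between-patient SD 6, 12 or 18, day-to-day SD 12; migraine-free-day mean 1;
- frequency reduction 10% on placebo and 30% on active;
- between-patient log-SD of month-3 frequency 0.2, 0.5 or 0.8;
- complete data.

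These give 2 x 3 x 3 = 18 scenarios. Method IV was approximated by regressing the month-3 average on treatment, baseline and stratum. The variance ratio is the residual variance with the Day 1 baseline divided by that with the average baseline.

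| | Lag-1 correlation of migraine days 0.4 | Independent days |
|---|---|---|
| Variance ratio, range | 1.02 to 1.41 | 1.03 to 1.77 |
| Standard error ratio (square root) | 1.01 to 1.19 | 1.01 to 1.33 |
| Largest difference in adjusted effect (points) | 0.02 | 0.02 |
| Largest difference in expected within-arm mean change (points) | 0.35 | 0.22 |
| Ratio of SDs of raw change | 2.1 to 3.0 | 2.3 to 3.8 |

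The correlated column is the more realistic, since protocol 1.1 describes headaches lasting 4 to 72 hours. The SD of raw change matters for descriptive tables only, because method IV adjusts for baseline.

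**Dependence on the model.** If each patient's underlying level is assumed not to change between baseline and month 3, the equal-correlation model gives a ratio of (1 - r²/v)/(1 - r²/v²). That is 1.5 at r = 0.05 and 7.6 at r = 0.5. It implies that the baseline average correlates 0.60 to 0.97 with month 3, with no variation between patients in response. It serves as an extreme, not as an estimate.

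**The case against.** The best reply is that the intent is already clear. SAP 2.1.2 is the section that defines endpoint terms, and it gives an explicit formula for each domain. Section 5.1.2 averages observed scores over the interval, and Table 5 calls both endpoints monthly. Section 2.10 reads as generic PRO text: it subtracts from a visit score and mentions a total score, although Appendix E.1 says MPFID has none. A specific formula normally prevails over general wording. This stands as the more plausible reading, but it is an inference. Section 2.1.1 itself lists MPFID under both rules, so the conflict is not confined to 2.10.

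Redaction is a second point. Text directly before MPFID in the second paragraph of 2.1.1 is hidden, as is text around 2.10, and the output shells are not available. Hidden words might limit the Day 1 rule. The visible sentences in 2.10 still state it and then name MPFID.

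Third, a reader might infer that 2.10 tells the programmer to subtract a one-day score from a monthly average. It does not. It subtracts from a visit score, and the pairing examined above combines the baseline of 2.10 with the month-3 value of 2.1.2. No single passage states that estimator. A fully literal 2.10 would compare two single scores, which the figures above do not cover.

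Fourth, the figures depend wholly on assumed inputs, and method IV was approximated at one month. That is correct, and it rules out converting the loss into a number of patients.

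**Conclusion.** The SAP contradicts itself on the baseline for two secondary endpoints, and nothing visible resolves it. The text favours the Baseline Epoch average. The severity is minor to moderate.

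If the Day 1 score were paired with the month-3 average, the cost would be precision. The variance of the adjusted contrast would rise by a factor of about 1.02 to 1.4 with correlated days, which widens confidence intervals by about 1% to 19%. With independent days the factor reaches about 1.8, or about 33% wider. These ranges hold only under the stated assumptions.

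Two stronger conclusions are tempting and are not supported. One is that the Day 1 rule biases the treatment comparison: baseline precedes randomized treatment under either rule, and the simulated adjusted effects agree to about 0.02 points. The other is that the trial is underpowered as a result: the sample size rests on the primary responder endpoint, which does not use MPFID.

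**What to change.** 1. Confirm that MPFID was collected daily in the Baseline Epoch. SAP 2.1.1 and Table 14 imply that it was. The wording in 2.1.2 ties daily completion to the double-blind epoch, and the daily entry in protocol Table 6-1 appears to start a column later than in SAP Table 14, although the table layout may have been damaged in text extraction. SAP 2.11 speaks only of daily eDiary use in general. Without that collection the 2.1.2 formulas cannot be computed, and the baseline needs a fresh definition.
2. If confirmed, remove MPFID from the PRO rule in the second Baseline paragraph of 2.1.1, and exempt it from the Day 1 sentence in 2.10.
3. State in both places that the MPFID baseline is the mean of observed daily domain scores from Week -4 to the day before Day 1, requiring at least 14 days with an observed domain score. That is the criterion in the daily-domain-score row of Table 8 in section 5.1.2 (its endpoint label is redacted). The text above the table counts days of eDiary use instead, so the criterion should be named.
4. Align the collection wording in 2.1.2.

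Make the change before unblinding. If the double-blind data are already unblinded, the report should say which baseline was programmed and show the result under the other. The cost is SAP wording only, with no change to the design, the primary analysis or the sample size.

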2.10.5 Migraine Physical Function Impact Diary (MPFID)

For each domain, the scores will be calculated as the sum of the item responses and the sum will be rescaled to a 0 to 100 scale, with higher scores representing greater impact of migraine (ie, higher burden). There will be a score for each of the two domains and a third score for the stand alone item.

No sensitivity analysis will be conducted for PROs.

2.11 Clinical Outcomes Assessments (COAs) and Electronic Diaries (eDiaries)
Clinical Outcomes Assessments (COAs) will be collected by subjects using a handheld electronic diary (eDiary). The eDiary will collect the following COAs:

- Incidence of headache (ie, migraine with or without aura or non-migraine headache)
- Time of onset of headache
- Time of resolution of headache
- Pain severity per headache
- Symptoms (eg, nausea, vomiting, photophobia, phonophobia)
- Presence of aura
- Use of acute medication during aura or to treat headache

Site study staff will assign and provide an eDiary to the subject at the week -4 visit (after confirming the subject's eligibility to enter the baseline phase). The site study staff will train the subject on how to use the eDiary (eg, turning on/off, charging, navigating screens, transmitting data, contacting the help desk for technical assistance) and complete the questions. The subject will be instructed to interact with the eDiary every day and to bring the eDiary to every study visit. Prior to randomization, the investigator will use the subject's eDiary to review all data entered during the baseline phase and confirm the relevant inclusion and exclusion criteria as noted in [Section 5.5](#).

[figure not shown]
A subject will interact with his/her eDiary each day during the baseline, double-blind treatment and open-label treatment epochs.

[figure not shown]
The subject's eDiary will also be used for the completion of the following patient-reported outcomes (PROs) measures:

- Migraine Physical Function Impact Diary (MPFID)

Assessment schedule and frequency of all PROs are in [Appendix D](#). Refer to the eDiary manual for details.

2.14 Interim analysis

Not applicable.

3 Sample size calculation

Assuming a treatment effect similar to the effect observed in a previous study 296 with AMG 334 in episodic migraine, the following sample size considerations apply.

Under 2-sided 0.05 alpha level, with 90% power, it takes 220 patients (110 per treatment group) to detect about an absolute 20% improvement on the response rate of 50% reduction on migraine days assuming 18% response rate in placebo group (equivalent of 2.8 in terms of odds ratio).

The power calculation is derived through nQuery 7.0.

4 Change to protocol specified analyses

1. The per-protocol (PP) analysis set, last observation carried forward (LOCF) method, inverse probability weighted (IPW) method using generalized estimate equation (GEE) to handle missing data will not be used as not informative for sensitivity purpose.

2. To evaluate the effect of AMG 334 compared to placebo the following additional endpoints were inserted:

- [Redacted]
- [Redacted]
- [Redacted]
- [Redacted]
- [Redacted]

4. Randomized Analysis Set (RAS) was defined to use for medical history, patient disposition, demographics and baseline characteristics.

5. [REDACTED]

5 Appendix

5.1 Imputation rules

Subjects may miss specific data points for a variety of causes. In general, data could be missing due to a subject's early withdrawal from study, a missed visit, or inability to evaluate an endpoint at a particular point in time. For this study, most of the efficacy endpoint will be collected via eDiary and subjects could miss entering several days of data in each 28-consecutive day interval. The general procedures outlined below describe what will be done when a data point is missing.

5.1.1 Study drug

Date of first study drug administration (Day 1)

Day 1 is defined as the first day of administration of randomized study drug (AMG334 or matching placebo). All other days will be labeled relative to Day 1. If subject will not be dosed at Day 1, the Study Day 1 is defined as day of randomization.

Date of last study drug administration

The date of last dose of randomized study drug is simply the day of the last dose.

5.1.2 eDiary data

The eDiary includes the following clinical outcome assessments:

- Incidence of headache (ie, migraine with or without aura or non-migraine headache)
- Time of onset of headache
- Time of resolution of headache
- Pain severity per headache
- Symptoms (eg, nausea, vomiting, photophobia, phonophobia)
- Presence of aura
- Use of acute medication during aura or to treat headache

As well as, patient-reported outcomes (PROs) measures of MPFID, [REDACTED]

Missing eDiary data in the calculation of monthly measurements about subjects' migraine and non-migraine headaches will be handled using the following method:

1. For monthly intervals with ≥ 14 days of eDiary days (including retrospective eDiary days) in each interval:

a) Monthly frequency measurements (including migraine days, headache days, [REDACTED] acute medication use, acute migraine specific medication use etc.) will be prorated to 28-day equivalents. Prorated result does not need to be rounded.

b) [REDACTED] impact on everyday activities scores as measured by MPFID will be calculated as the average of observed scores

2. For monthly intervals with < 14 days of eDiary use (including retrospective eDiary days), all monthly measurement will be set as missing and will be handled as described in [Section 5.1.6](#).

Table 8 Rules for handling missing and incomplete eDiary data

Monthly Endpoint	Condition	Proration Method (does not need to be rounded)
Monthly frequency measurements (including migraine days, headache days, [REDACTED] hours of migraine headaches, acute headache medication treatment days, acute migraine-specific medication treatment days)	If diary days in entire baseline or interval post baseline ≥ 14 (including retrospective eDiary days), then do proration; Else monthly measurement is set to missing [diary days is a day with all headache related questions completed retrospectively or not]	Number of observed migraine days * 28/ Number of information days in interval [information day is a diary day or headache day]
[REDACTED]	If days with observed daily domain score in interval ≥ 14 then calculate the average; Else missing	Arithmetic mean of the observed daily domain score over the monthly interval
[REDACTED]	[REDACTED]	[REDACTED]

Missing PROs scheduled to be collected at office visit at certain assessment will not be imputed.

Missing safety endpoints will not be imputed. Missing day portion of AE start time will be imputed based on next [Section 5.1.3](#).

Missing anti-AMG 334 antibody data will not be imputed.

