Number of headache days between each monthly IP dose. Monthly headache days at baseline are the number of headache days in baseline period. Days without eDiary data in each monthly interval are handled by proration according to [Section 5.1.2](#).

Monthly Acute Headache Medication Treatment Days

Number of days on which acute headache medications are used as recorded in eDiary between each monthly IP dose. Monthly acute headache medication treatment days at baseline are the number of acute headache medication treatment days in the baseline period. Days without eDiary data are handled by proration according to [Section 5.1.2](#).

[REDACTED]

[REDACTED]

Monthly Acute Migraine-Specific Medication Treatment Days

Number of days on which acute migraine-specific medications are used as recorded in eDiary between each monthly IP dose. Migraine-Specific medications include two categories of medications: triptan-based migraine medications and ergotamine-based migraine medications. Monthly migraine-specific medication use at baseline is the number of migraine-specific medication treatment days in the baseline period. Days without eDiary data are handled by proration according to [Section 5.1.2](#).

Change from baseline in monthly acute migraine-specific medication treatment days in the last month of the double-blind treatment epoch

Calculated based on the following: (monthly acute migraine-specific medication treatment days in the last month of the DBTE) – (baseline monthly acute migraine-specific medication treatment days)

Response

At least 50% (or 75%, 100%) reduction from baseline in monthly migraine days.

[REDACTED]

[REDACTED]

[REDACTED]

[REDACTED]

[REDACTED]

Migraine Physical Function Impact Diary (MPFID)

The Migraine Physical Function Impact Diary (MPFID) is a self-administered 13-item instrument measuring physical functioning. It has two domains, Impact on Everyday Activities (7 items) and Physical Impairment (5 items), and one stand-alone global question which provides an assessment of overall impact on everyday activities. Subjects respond to items using a 5-point scale, with difficulty items ranging from “Without any difficulty” to

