2.6 Analysis of secondary efficacy objectives

2.6.1 Secondary endpoints

The secondary endpoints during double-blind treatment epoch are:

- Change from baseline in monthly migraine days in the last month (month 3) of the double-blind treatment epoch
- Change from baseline in “impact on everyday activities” domain as measured by the MPFID in the last month (month 3) of the double-blind treatment epoch
- Change from baseline in “physical impairment” domain as measured by the MPFID in the last month (month 3) of the double-blind treatment epoch
- Change from baseline in acute monthly migraine-specific treatment days in the last month (month 3) of the double-blind treatment epoch
- The achievement of at least a 75% reduction from baseline in monthly migraine days in the last month (month 3) of the double-blind treatment epoch
- The achievement of a 100% reduction from baseline in monthly migraine days in the last month (month 3) of the double-blind treatment epoch

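### The proration formula in SAP 5.1.2, Table 8 puts migraine days in the numerator for every monthly frequency measure, which conflicts with the definition of the secondary endpoint on acute migraine-specific medication days

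*SAP*

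**What the plan says.** SAP 2.6.1 lists as a secondary endpoint "Change from baseline in acute monthly migraine-specific treatment days in the last month (month 3) of the double-blind treatment epoch". SAP 2.1.2 defines the underlying monthly measure as "Number of days on which acute migraine-specific medications are used as recorded in eDiary between each monthly IP dose", limits it to triptan-based and ergotamine-based drugs, and refers to Section 5.1.2 for days without diary data.

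Section 5.1.2 handles incomplete diaries in two places:

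- **Text rule 1(a).** For intervals with at least 14 diary days, a list of measurements that includes "acute medication use, acute migraine specific medication use etc.) will be prorated to 28-day equivalents". It names no numerator.
- **Table 8, first row.** This row covers the monthly frequency measurements, beginning with migraine days and headache days and continuing with "hours of migraine headaches, acute headache medication treatment days, acute migraine-specific medication treatment days". The only formula in the row is "Number of observed migraine days * 28/ Number of information days in interval". The denominator is explained by the note "information day is a diary day or headache day". The condition for using the formula is at least 14 diary days in the interval, "including retrospective eDiary days), then do proration".

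The visible redaction in this row is in the list of measures. The formula cell shows none.

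**The concern.** Table 8 is the only place in Section 5.1.2 that writes out a calculation for these measures, and SAP 2.1.2 sends the medication-day endpoint there. The numerator fits migraine days and none of the other measures in the row. A programmer who copied the cell would give the medication endpoint the migraine-day value.

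Protocol 6.4.3 treats reduced use of acute migraine-specific medication as an important secondary outcome because frequent rescue use can lead to medication-overuse headache. If the endpoint took the migraine-day value, the report would show the migraine-day effect twice under two labels. The baseline summaries of monthly headache days and acute medication days in SAP 2.3.2 would be open to the same error.

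**Working it through.** The plan states no figure to reproduce, so the check sets the printed formula against each measure's own definition. All diary counts below are assumptions chosen for illustration.

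**Formulas**

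- As printed, for any measure in the row: migraine days × 28 / information days.
- As SAP 2.1.2 implies: the measure's own count × 28 / information days.

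The 14-day condition and the denominator are common to the whole row. Under the printed formula the medication-day value therefore equals the migraine-day value at baseline and at each later interval in which the formula is used.

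**Single intervals**

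| Information days | Migraine days | Medication days | Medication value as printed | Medication value from own count |
|---|---|---|---|---|
| 28 | 8 | 4 | 8 × 28/28 = 8.0 | 4 × 28/28 = 4.0 |
| 24 | 6 | 4 | 6 × 28/24 = 7.00 | 4 × 28/24 = 4.67 |
| 14 | 8 | 0 | 8 × 28/14 = 16.0 | 0 |
| 28 | 6 | 6 | 6 × 28/28 = 6.0 | 6 × 28/28 = 6.0 |

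In the second line, add 8 headache days. The printed formula gives 7.00 for headache days as well, against 8 × 28/24 = 9.33. The last line shows that the two formulas agree when every migraine day is also a medication day.

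**Change from baseline**

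Assume 9 migraine and 5 medication days over 28 information days at baseline, then 5 migraine and 2 medication days over 26 information days at month 3.

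- Monthly migraine days: 5 × 28/26 − 9 × 28/28 = 5.38 − 9.00 = −3.62.
- Medication days as printed: the same, −3.62.
- Medication days from own count: 2 × 28/26 − 5 × 28/28 = 2.15 − 5.00 = −2.85.

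**Measures not affected**

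The 50%, 75% and 100% responder endpoints and change in monthly migraine days are built on migraine days, for which the numerator is right. MPFID is an average of observed scores under a separate rule in Section 5.1.2.

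**The case against.** The strongest reply is that the SAP already settles the intended numerator. SAP 2.1.2 defines the medication endpoint by days of medication use and calls on Section 5.1.2 only for days without diary entries. Rule 1(a) speaks of prorating each measurement itself, which cannot sensibly mean replacing it with another. SAP 2.1.2 introduces proration under migraine days and extends the same method to the other endpoints, so the Table 8 cell reads naturally as the migraine-day case standing for the row. The literal reading also fails within its own row, since a count of migraine days cannot produce hours of migraine headache. This reply stands as to intent, and a careful programmer would probably use the right count. It does not make the printed formula correct.

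A reader might infer more than the documents support, in three ways:

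- **That the endpoint would carry no information on medication use.** Under SAP 2.1.2, a day on which a triptan or ergotamine is taken during aura or for a headache counts as a migraine day. The migraine-day count therefore includes those medication days, even on the literal reading.
- **That the eligibility limits guarantee a minimum overstatement at baseline.** With 10 to 14 baseline migraine days and triptan or ergotamine use below 10 days a month, one might deduce an error of at least 1 to 5 days. That bound fails. Ten against nine days over 32 information days differ by (10 − 9) × 28/32 = 0.875, and SAP 2.4.1 allows for baseline intervals longer than 28 days. Exclusion 7 works in calendar months, and the patient classification table in SAP 5.5 removes no one from the FAS for a protocol deviation, so a patient who breached that limit stays in.
- **That every month with a complete diary is certainly affected.** Table 8's condition does take in complete diaries. However, SAP 2.1.2 invokes proration of medication days only for days without data, and its explicit 28-day normalisation is attached to migraine days. How far complete months are affected depends on which text is followed.

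**Conclusion.** The point holds as a conflict within the SAP. The one formula printed for a row that includes a named secondary endpoint does not compute that endpoint as SAP 2.1.2 defines it. Followed literally, it gives the medication endpoint the value of monthly migraine days. The error for a patient is the gap between migraine days and medication days, scaled to 28 days: zero where every migraine day is a medication day, and 4.0 days in the illustration of 8 against 4 over 28 information days. The documents give no distribution of medication days, so an average error cannot be stated.

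It would be wrong to conclude that the endpoint was miscomputed. The definition shows what was meant, and nothing in the documents shows which count the program used. Among the named efficacy endpoints, the conflict touches only this secondary endpoint.

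**What to change.** In Table 8 of SAP 5.1.2, replace the numerator with: number of observed days (or hours) of the respective measurement in the interval. Spell it out for the secondary endpoint: observed acute migraine-specific medication treatment days × 28 / information days. Then confirm that the derivation program uses each measure's own count, for headache days, hours of migraine headache and acute headache medication days as well as for the secondary endpoint.

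The cost is one line of SAP text with an entry in its change log, plus a short program check. No new data are needed. The protocol text available contains no proration formula, so no protocol amendment follows from this.
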